Anti-epileptic mood stabilizers	Lipid lowering drugs
Anti-epileptics (other than mood stabilizers)	Non-insulin diabetes medications
Atypical antipsychotics	Insulin
Benzodiazepines	Antidepressants
Serotonin-norepinephrine reuptake Inhibitors	Typical antipsychotics
Selective serotonin reuptake inhibitors	Anticoagulants
Tricyclic antidepressants (TCAs)	Antiplatelet agents

Comorbid conditions	
Atrial fibrillation	Chronic liver disease
Coronary artery disease	Asthma
Heart failure	Ischemic heart disease
Stroke or transient ischemic attack	Chronic obstructive pulmonary disease
Peripheral vascular disease	Malignancy
Hyperlipidemia	Drug or alcohol abuse or dependence
Renal dysfunction	Venous thromboembolism

ICD-9, ICD-10, HCPCS, and NDC codes used to define the covariates listed above are available in Appendix A.

c. Outcome variables and study follow-up:

- **Primary outcome:** incident dementia, i.e., Alzheimer's disease, vascular dementia, senile, presenile, or unspecified dementia, or dementia in other diseases classified elsewhere. Outcome will be defined by 1 inpatient claim or 2 outpatient claims in analysis 1, 2, 3. In analysis 4, the outcome will be defined by 1 inpatient or 1 outpatient claims and 1 prescription claim for a symptomatic treatment [donepezil, galantamine, rivastigmine, and memantine] within 6 months of each other with outcome date assigned to second event in the sequence.

- Secondary outcomes: Individual component:
Alzheimer's disease

Condition	ICD-9 and ICD-10 codes
Alzheimer's disease	331.0*, F00*, G30*
Vascular dementia	290.4*, F01*
Senile, presenile, or unspecified dementia	290.0*, 290.1*. 290.3*, 797*, F03*
Dementia in other diseases classified elsewhere	331.1*, 331.2*, 331.7*, 294.1*, F02*

For analysis 1,3, and 4 the follow-up will start the day after initiation of Propranolol or Carvedilol and Atenolol, Bisoprolol or Sotalol and will continue until the earliest date of the following events:

- The first occurrence of the outcome of interest
- The date of end of continuous registration in the database,
- End of the study period,
- Measured death event occurs,
- The date of drug discontinuation, defined as the date of the last continuous treatment episode of the index drug (Propranolol or Carvedilol and hydrochlorothiazide) plus a defined grace period (i.e., 90 days after the end of the last prescription's days' supply in main analyses).

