For analysis 2, the follow-up will start 180 days after initiation of Propranolol or Carvedilol and Atenolol, Bisoprolol or Sotalol and will continue until the earliest date of the following events:

- The first occurrence of the outcome of interest, unless otherwise specified for selected outcomes,
- The date of end of continuous registration in the database,
- End of the study period,
- Measured death event occurs,
- Maximum allowed follow-up time (1095 days) reached

7. Propensity score analysis

We will use a propensity-score (PS)¹-based approach to account for measured confounding in this study. The PS will be calculated as the predicted probability of initiating the exposure of interest (i.e., the repurposing candidate) versus the reference drug conditional on baseline covariates using multivariable logistic regression constructed separately in each data source. On average, patients with similar PSs have similar distribution of potential confounders used to estimate the PS. Therefore, analyses conditioned on the PS provide effect estimates that are free from measured confounding. For all our analyses, initiators of each exposure of interest will be matched with initiators of the reference exposure based on their PS within each data source.² Pair matching will be conducted using a nearest-neighbor algorithm, which seeks to minimize the distance between propensity scores in each pair of treated and reference patients,³ and a caliper of 0.025 on the natural scale of the PS will be used to ensure similarity between the matched patients.⁴

We report multiple diagnostics for PS analysis in this protocol. First, the PS distributional overlap is provided between two groups before and after matching to ensure comparability of these groups.⁵ Next, balance in each individual covariate between two treatment groups is reported using standardized differences.⁶

8. Table for covariate balance

Variable	Crude			PS-Matched		
	Propranolol and Carvedilol (N = 583,870)	Atenolol, Bisoprolol, Sotalol (N = 233,467)	St. Diff	Propranolol and Carvedilol (N = 222,015)	Atenolol, Bisoprolol, Sotalol (N = 222,015)	St. Diff
Demographics						
Age, mean (SD)	75.02 (7.00)	74.75 (6.77)	0.04	74.77 (6.82)	74.75 (6.78)	0.00
Gender, n (%)						
Male	281,232 (48.2%)	97,628 (41.8%)	0.13	93,749 (42.2%)	94,142 (42.4%)	0.00
Female	302,638 (51.8%)	135,839 (58.2%)	-0.13	128,266 (57.8%)	127,873 (57.6%)	0.00
Race, n (%)						

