White	451,438 (77.3%)	186,360 (79.8%)	-0.06	177,198 (79.8%)	176,941 (79.7%)	0.00
Black	79,181 (13.6%)	23,050 (9.9%)	0.12	22,448 (10.1%)	22,557 (10.2%)	0.00
Hispanic	18,869 (3.2%)	7,616 (3.3%)	-0.01	7,289 (3.3%)	7,209 (3.2%)	0.01
Asian	16,471 (2.8%)	8,738 (3.7%)	-0.05	7,954 (3.6%)	8,042 (3.6%)	0.00
North American Native	3,845 (0.7%)	1,494 (0.6%)	0.01	1,347 (0.6%)	1,426 (0.6%)	0.00
Other	10,192 (1.7%)	4,575 (2.0%)	-0.02	4,242 (1.9%)	4,273 (1.9%)	0.00
Unknown	3,874 (0.7%)	1,634 (0.7%)	0.00	1,537 (0.7%)	1,567 (0.7%)	0.00
Region, n (%)						
Northeast; n (%)	79,800 (13.7%)	41,038 (17.6%)	-0.11	37,554 (16.9%)	37,805 (17.0%)	0.00
South; n (%)	275,558 (47.2%)	102,251 (43.8%)	0.07	99,500 (44.8%)	98,821 (44.5%)	0.01
Midwest; n (%)	127,682 (21.9%)	49,611 (21.2%)	0.02	47,379 (21.3%)	47,515 (21.4%)	0.00
West; n (%)	99,172 (17.0%)	39,516 (16.9%)	0.00	37,582 (16.9%)	37,874 (17.1%)	-0.01
Other; n (%)	1,658 (0.3%)	1,051 (0.5%)	-0.03			
Calendar year of index date, n (%)						
2008	41,242 (7.1%)	22,822 (9.8%)	-0.10	21,021 (9.5%)	20,784 (9.4%)	0.00

DREAM study protocol - Comparison 13 Propranolol or Carvedilol vs Atenolol, Bisoprolol, Sotalol

2009	41,633 (7.1%)	23,317 (10.0%)	-0.10	21,612 (9.7%)	21,325 (9.6%)	0.00
2010	33,970 (5.8%)	14,179 (6.1%)	-0.01	13,633 (6.1%)	13,538 (6.1%)	0.00
2011	31,276 (5.4%)	12,573 (5.4%)	0.00	12,160 (5.5%)	12,081 (5.4%)	0.00
2012	29,262 (5.0%)	11,653 (5.0%)	0.00	11,275 (5.1%)	11,283 (5.1%)	0.00
2013	79,415 (13.6%)	36,290 (15.5%)	-0.05	34,117 (15.4%)	34,212 (15.4%)	0.00
2014	77,490 (13.3%)	32,016 (13.7%)	-0.01	30,163 (13.6%)	30,408 (13.7%)	0.00
2015	71,638 (12.3%)	27,434 (11.8%)	0.02	26,098 (11.8%)	26,324 (11.9%)	0.00
2016	48,353 (8.3%)	15,916 (6.8%)	0.06	15,423 (6.9%)	15,491 (7.0%)	0.00
2017	42,820 (7.3%)	12,385 (5.3%)	0.08	12,062 (5.4%)	12,146 (5.5%)	0.00
2018	44,058 (7.5%)	12,714 (5.4%)	0.09	12,447 (5.6%)	12,493 (5.6%)	0.00
2019	42,713 (7.3%)	12,168 (5.2%)	0.09	12,004 (5.4%)	11,930 (5.4%)	0.00
Low income subsidy, n (%)	163,393 (28.0%)	60,269 (25.8%)	0.05	58,330 (26.3%)	58,026 (26.1%)	0.00
Dementia risk factors, n (%)						
Anxiety	88,780 (15.2%)	33,787 (14.5%)	0.02	32,757 (14.8%)	32,295 (14.5%)	0.01
Bipolar disorder	6,969 (1.2%)	2,315 (1.0%)	0.02	2,299 (1.0%)	2,263 (1.0%)	0.00
Coronary artery disease	333,862 (57.2%)	99,371 (42.6%)	0.30	96,483 (43.5%)	96,613 (43.5%)	0.00
Depression	93,473 (16.0%)	33,665 (14.4%)	0.04	32,918 (14.8%)	32,329 (14.6%)	0.01
Diabetes, n (%)	451,149 (77.3%)	176,186 (75.5%)		168,274 (75.8%)	168,200 (75.8%)	0.00

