Obesity	148,289 (25.4%)	50,211 (21.5%)	0.09	48,216 (21.7%)	48,375 (21.8%)	0.00
Schizophrenia	3,054 (0.5%)	1,101 (0.5%)	0.00	1,045 (0.5%)	1,064 (0.5%)	0.00
Markers for healthy behavior, frailty, healthcare use						
Bone mineral density test, n (%)	247 (0.0%)	135 (0.1%)	-0.04	141 (0.1%)	123 (0.1%)	0.00
Colonoscopy, n (%)	64,492 (11.0%)	26,148 (11.2%)	-0.01	24,751 (11.1%)	24,752 (11.1%)	0.00
Fecal occult blood test, n (%)	43,860 (7.5%)	19,665 (8.4%)	-0.03	18,342 (8.3%)	18,285 (8.2%)	0.00
Influenza vaccination, n (%)	355,785 (60.9%)	143,137 (61.3%)	-0.01	136,240 (61.4%)	136,167 (61.3%)	0.00

DREAM study protocol - Comparison 13 Propranolol or Carvedilol vs Atenolol, Bisoprolol, Sotalol

Mammography, n (%)	87,549 (15.0%)	43,295 (18.5%)	-0.09	40,715 (18.3%)	40,590 (18.3%)	0.00
Pneumococcal vaccination, n (%)	169,570 (29.0%)	55,949 (24.0%)	0.11	54,070 (24.4%)	54,269 (24.4%)	0.00
Smoking, n (%)	177,079 (30.3%)	54,670 (23.4%)	0.16	52,411 (23.6%)	52,816 (23.8%)	0.00
Number of C-reactive protein tests ordered, mean (SD)	0.21 (0.81)	0.21 (0.81)	0.00	0.21 (0.86)	0.21 (0.80)	0.00
Number of emergency room visits, mean (SD)	1.87 (3.20)	1.50 (2.71)	0.12	1.51 (3.04)	1.51 (2.69)	0.00
Number of distinct prescriptions, mean (SD)	14.66 (6.45)	13.23 (6.36)	0.22	13.44 (6.02)	13.34 (6.39)	0.02
Number of hospitalizations, mean (SD)	0.90 (1.23)	0.61 (1.02)	0.26	0.61 (1.00)	0.62 (1.03)	-0.01
Number of outpatient visits, mean (SD)	14.81 (17.01)	15.01 (18.07)	-0.01	15.04 (19.64)	14.87 (17.37)	0.01
Number of physician office visits, mean (SD)	5.43 (10.24)	5.76 (11.48)	-0.03	5.77 (12.39)	5.68 (10.95)	0.01
Number of Cardiologist visits, mean(SD)	4.28 (5.14)	3.70 (5.00)	0.11	3.66 (4.93)	3.67 (4.98)	0.00
Number of serum creatinine tests ordered, mean (SD)	4.37 (3.94)	3.85 (3.32)	0.14	3.90 (3.48)	3.88 (3.34)	0.01
Composite frailty score, mean (SD)	0.22 (0.06)	0.20 (0.06)	0.33	0.20 (0.06)	0.20 (0.06)	0.00
Falls, n (%)	29,969 (5.1%)	10,173 (4.4%)	0.03	9,818 (4.4%)	9,782 (4.4%)	0.00
Fractures, n (%)	41,635 (7.1%)	15,605 (6.7%)	0.02	14,813 (6.7%)	14,855 (6.7%)	0.00
Osteoporosis, n (%)	63,351 (10.9%)	28,996 (12.4%)	-0.05	27,367 (12.3%)	27,019 (12.2%)	0.00
Use of supplemental oxygen, n (%)	21,888 (3.7%)	5,840 (2.5%)	0.07	5,735 (2.6%)	5,696 (2.6%)	0.00
Combined comorbidity score, mean (SD)	5.66 (3.07)	4.41 (2.76)	0.43	4.48 (2.71)	4.47 (2.79)	0.00
Comedication use, n (%)						

DREAM study protocol - Comparison 13 Propranolol or Carvedilol vs Atenolol, Bisoprolol, Sotalol

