Antidepressants	155,811 (26.7%)	57,867 (24.8%)	0.04	56,683 (25.5%)	55,691 (25.1%)	0.01
Insulin	136,095 (23.3%)	36,934 (15.8%)	0.19	36,455 (16.4%)	36,240 (16.3%)	0.00
Lipid lowering drugs	443,656 (76.0%)	163,735 (70.1%)	0.13	157,484 (70.9%)	157,194 (70.8%)	0.00
Nitrates	128,629 (22.0%)	33,284 (14.3%)	0.20	32,638 (14.7%)	32,626 (14.7%)	0.00
Non-insulin diabetes medications	310,939 (53.3%)	122,525 (52.5%)	0.02	117,674 (53.0%)	117,427 (52.9%)	0.00
Anticoagulants	107,632 (18.4%)	55,118 (23.6%)	-0.13	49,968 (22.5%)	49,752 (22.4%)	0.00
Anti-epileptic mood stabilizers	8,005 (1.4%)	2,725 (1.2%)	0.02	2,764 (1.2%)	2,658 (1.2%)	0.00
Antiplatelet agents	146,057 (25.0%)	38,480 (16.5%)	0.21	37,748 (17.0%)	37,750 (17.0%)	0.00
Atypical antipsychotics	11,643 (2.0%)	4,105 (1.8%)	0.01	4,059 (1.8%)	3,978 (1.8%)	0.00
Benzodiazepines	74,533 (12.8%)	28,965 (12.4%)	0.01	28,241 (12.7%)	27,664 (12.5%)	0.01
Lithium	797 (0.1%)	237 (0.1%)	0.00	228 (0.1%)	233 (0.1%)	0.00
Anti-epileptics (other than mood stabilizers)	108,520 (18.6%)	35,720 (15.3%)	0.09	35,144 (15.8%)	34,621 (15.6%)	0.01
Serotonin-norepinephrine reuptake inhibitors	29,400 (5.0%)	10,743 (4.6%)	0.02	10,731 (4.8%)	10,428 (4.7%)	0.00
Selective serotonin reuptake inhibitors	93,719 (16.1%)	34,751 (14.9%)	0.03	33,965 (15.3%)	33,404 (15.0%)	0.01
Tricyclic antidepressants (TCAs)	25,906 (4.4%)	10,286 (4.4%)	0.00	10,022 (4.5%)	9,858 (4.4%)	0.00
Typical antipsychotics	2,396 (0.4%)	942 (0.4%)	0.00	924 (0.4%)	905 (0.4%)	0.00
Comorbid conditions, n (%)						
Atrial fibrillation	153,296 (26.3%)	79,342 (34.0%)	-0.17	71,905 (32.4%)	71,714 (32.3%)	0.00
Asthma	104,291 (17.9%)	35,409 (15.2%)	0.07	34,135 (15.4%)	33,885 (15.3%)	0.00
Chronic obstructive pulmonary disease	175,599 (30.1%)	58,758 (25.2%)	0.11	56,819 (25.6%)	56,347 (25.4%)	0.00
Chronic liver disease	52,786 (9.0%)	17,419 (7.5%)	0.05	16,869 (7.6%)	16,796 (7.6%)	0.00

DREAM study protocol - Comparison 13 Propranolol or Carvedilol vs Atenolol, Bisoprolol, Sotalol

Drug or alcohol abuse or dependence	77,453 (13.3%)	23,239 (10.0%)	0.10	22,489 (10.1%)	22,579 (10.2%)	0.00
Heart failure	279,855 (47.9%)	60,940 (26.1%)	0.46	60,752 (27.4%)	60,584 (27.3%)	0.00
Hyperlipidemia	510,009 (87.3%)	201,744 (86.4%)	0.03	192,105 (86.5%)	191,970 (86.5%)	0.00
Ischemic heart disease	348,401 (59.7%)	107,358 (46.0%)	0.28	104,109 (46.9%)	104,139 (46.9%)	0.00
Malignancy	156,428 (26.8%)	62,247 (26.7%)	0.00	59,313 (26.7%)	58,882 (26.5%)	0.00

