Peripheral vascular disease	129,600 (22.2%)	40,710 (17.4%)	0.12	39,670 (17.9%)	39,327 (17.7%)	0.01
Renal dysfunction	236,212 (40.5%)	56,863 (24.4%)	0.35	56,068 (25.3%)	56,128 (25.3%)	0.00
Stroke or transient ischemic attack	68,173 (11.7%)	23,278 (10.0%)	0.05	22,586 (10.2%)	22,216 (10.0%)	0.01
Venous thromboembolism	37,549 (6.4%)	11,617 (5.0%)	0.06	11,391 (5.1%)	11,122 (5.0%)	0.00

9. Statistical analysis plans

Incidence rates for the outcome will be estimated for the treatment and reference groups before and after PS matching. The competing risk of death could be of concern for the current set of analyses if mortality is frequent among patients included in the cohort and if differences in the risk of mortality between treatment and reference groups are substantial. In the PS-matched sample, we will use cause-specific hazard models⁷ to provide hazard ratios averaged over the entire follow-up period as well as interval specific hazard ratios (1, 2, and 3 years) for the association between the treatment of interest and risk of ADRD after considering all-cause mortality as a competing event. Pre-specified subgroup analyses will be conducted based on age, sex, and baseline cardiovascular disease. In addition to the Medicare dataset, we will pursue a similar analysis within Clinical Practice Research Datalink (CPRD), a UK population health dataset, to validate our results.

10. References

4. Austin PC. Some Methods of Propensity-Score Matching had Superior Performance to Others: Results of an Empirical Investigation and Monte Carlo simulations. *Biometrical Journal*. 2009;51(1):171-184.

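### Heart failure, the largest imbalance before matching, enters the propensity score only as present or absent, so balance on its type and severity is undocumented

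*Combined protocol and SAP*

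**What the plan says.** Section 1a sets the aim as comparing dementia risk between two pooled beta-blocker groups used for hypertension: propranolol or carvedilol, against atenolol, bisoprolol or sotalol. Section 5b requires hypertension claims in the year before index and does not exclude heart failure.

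Section 6b names heart failure once among the comorbid conditions (the two-column row reads "Heart failure Ischemic heart disease"), with no split by type or severity. On definitions it says: "ICD-9, ICD-10, HCPCS, and NDC codes used to define the covariates listed above are available in Appendix A". That appendix is not part of the text available here.

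Section 7 fits a logistic propensity score on the baseline covariates and pair-matches on the score within a caliper of 0.025. It then states: "Therefore, analyses conditioned on the PS provide effect estimates that are free from measured confounding".

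Section 8 reports heart failure as one count-and-percentage row: "Heart failure 279,855 (47.9%) 60,940 (26.1%) 0.46 60,752 (27.4%) 60,584 (27.3%) 0.00".

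Section 9 plans subgroups by age, sex and baseline cardiovascular disease. It does not define the last of these, and it states no analysis in patients free of heart failure.

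**The concern.** The covariate most strongly associated with drug choice is also one of the most coarsely measured. A yes/no flag can be perfectly balanced while the patients behind it differ in type of heart failure, recent decompensation or device therapy. None of these is a listed covariate. The comedication list includes nitrates but no diuretic, renin-angiotensin drug, mineralocorticoid antagonist or digoxin that could stand in for them.

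Type and severity could matter in two ways that the plan itself makes relevant. In analyses 1 to 3 a single inpatient claim is enough to define dementia (Section 6c), so unequal admission rates could change detection. Section 9 also says that competing mortality is a concern if it differs between groups, and unequal severity could produce such a difference. These mechanisms need not act in the same direction. The assurance in Section 7 covers measured confounding only, and type and specific severity are not measured.

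**Working it through.** **Inputs (Section 8).** Crude arms: 583,870 exposed and 233,467 comparator. Matched arms: 222,015 each. Heart failure: crude 279,855 and 60,940; matched 60,752 and 60,584.

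**1. Reproduce the plan's figures.** Standardized difference = (p1 − p0) / √[(p1(1−p1) + p0(1−p0))/2].
- Crude: p1 = 279,855/583,870 = 0.4793 and p0 = 60,940/233,467 = 0.2610, giving 0.464 (printed 0.46).
- Matched: p1 = 60,752/222,015 = 0.2736 and p0 = 60,584/222,015 = 0.2729, giving 0.002 (printed 0.00).

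Both agree with the table.

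**2. Rank.** The next largest crude differences are:
- comorbidity score: "Combined comorbidity score, mean (SD) 5.66 (3.07) 4.41 (2.76) 0.43"
- renal dysfunction: "Renal dysfunction 236,212 (40.5%) 56,863 (24.4%) 0.35"
- frailty score: 0.33
- coronary artery disease: "Coronary artery disease 333,862 (57.2%) 99,371 (42.6%) 0.30"

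Diabetes has no printed crude difference. Its counts give 0.04, so the ranking stands.

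**3. Strength of the tie to drug choice.** Without heart failure: 583,870 − 279,855 = 304,015 exposed, and 233,467 − 60,940 = 172,527 comparator. Crude odds ratio = (279,855/304,015) / (60,940/172,527) = 0.9205/0.3532 = 2.6.

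**4. What matching does.**

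| | Exposed kept | Comparator kept |
|---|---|---|
| Heart failure | 60,752/279,855 = 21.7% | 60,584/60,940 = 99.4% |
| No heart failure | 161,263/304,015 = 53.0% | 161,431/172,527 = 93.6% |

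Selection within heart failure is heavy and one-sided. Pairs are formed on the score, not on heart failure itself. The matched counts differ by 60,752 − 60,584 = 168, so at least 168 pairs are discordant on the diagnosis.

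**5. Illustrative size (assumed inputs).** Let h = (60,752 + 60,584)/(2 × 222,015) = 0.273. Let q1 and q0 be the shares of exposed and comparator heart-failure patients with an unmeasured type or severity, and RR its dementia rate ratio. All other patients are taken to share one baseline rate. Bias factor = [1 + h·q1(RR−1)] / [1 + h·q0(RR−1)].

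| q1 vs q0 | RR 1.2 | RR 1.5 | RR 2.0 |
|---|---|---|---|
| 0.5 vs 0.4 | 1.005 | 1.013 | 1.025 |
| 0.7 vs 0.4 | 1.016 | 1.039 | 1.074 |
| 0.8 vs 0.3 | 1.027 | 1.066 | 1.126 |

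For example, 0.7 vs 0.4 with RR 1.5 gives 1.0956/1.0547 = 1.039. Swapping q1 and q0, or taking RR below 1, turns the shift the other way. None of q1, q0 or RR comes from the documents.

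**6. Cost of a restricted analysis.** Taking the present match as a guide, 161,263 exposed and 161,431 comparator patients have no heart failure. That is about 27% fewer pairs. With similar event rates, interval width grows by √(222,015/161,263) = 1.17.

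**The case against.** The strongest reply is that the score already holds many correlates of cardiac severity: hospitalizations, emergency visits, cardiologist visits, creatinine tests, frailty, comorbidity score, supplemental oxygen, renal dysfunction, coronary disease and nitrates. After matching, all are within 0.01 in absolute standardized difference. Baseline hospitalizations are 0.61 against 0.62. The 21.7% of exposed heart-failure patients who are kept are those whose measured profile resembles the comparators, so the crude imbalance does not describe the analysed cohort. This stands, and it lowers the concern. It does not settle it, because these are averages over the whole cohort. None is specific to heart failure or shown among heart-failure patients.

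It can also be said that Appendix A might hold finer definitions. The code list behind the flag cannot be checked here, but the covariate list and the balance table each carry only one heart-failure item.

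A reader might infer more than the documents allow:
- **That carvedilol is chosen for reduced-ejection-fraction disease, so matched exposed patients have a different kind of heart failure.** The documents say nothing about why any drug was chosen. The arms pool propranolol with carvedilol and set them against three drugs including bisoprolol, and no drug-specific counts are given.
- **That 47.9% prevalence shows the drug was given for heart failure rather than hypertension.** A comorbidity is not an indication, and every patient needs hypertension claims to enter.
- **That the cardiovascular subgroup mixes heart failure with other conditions.** It is undefined. If it does include heart failure, its complement would be free of heart failure, but it would also exclude other cardiovascular disease. The plan does not state this.

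**Conclusion.** The point holds as a gap in measurement and reporting. Heart failure is the largest crude imbalance (0.46), is recorded only as present or absent, and affects about 27% of each matched arm. Balance on its type and specific severity is therefore not shown.

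That a difference exists within heart failure is an assumption. Under assumed inputs the hazard ratio moves by about 0.5% to several percent, reaching 13% only in the most extreme combination tried. The direction is open. The documents give no subtype data and no event counts, so the shift cannot be estimated or compared with the width of the planned interval. The 60,752 and 60,584 patients are those carrying the flag, not patients shown to be mismatched.

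**What to change.** 1. **Section 6b, with Sections 7 and 8.** Add claims-based heart-failure type (systolic, diastolic, unspecified), cardiomyopathy, implanted cardiac device, and heart-failure hospitalization in the 365 days before index. Re-estimate the score and re-match. Report balance on these items among heart-failure patients as well as overall. State how many fall in the unspecified type, since a large share would limit what the split achieves.
2. **Section 9.** Pre-specify a re-matched sensitivity analysis restricted to patients with no heart-failure code before index, as the version closest to the hypertension aim. Define baseline cardiovascular disease and say whether it includes heart failure. If outcome results have already been seen when these are added, label them post hoc.

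**Cost.** Extra code lists from claims already held, one re-match of the main cohort and one restricted run. The restricted run has about 27% fewer pairs and an interval about 17% wider, assuming similar event rates and the same look-back as the present flag. A longer look-back would remove more patients.
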